
Sponsor: Wave Life Sciences	Investigational Product: WVE-120101	Phase: 1b/2a	EudraCT Number: 2016-005095-10

16. Deemed to be at significant risk for suicidal behavior based on:
 

a The opinion of the Investigator; or

b Answers “yes” to Actual Suicide Attempts or Suicidal Behaviors in the Suicidal Behaviors section of the Columbia-Suicide Severity Rating Scale (C-SSRS) with reference to a 2-year period prior to the Screening Visit; or

c Answers “yes” on any items in the Suicidal Ideation section of the C-SSRS with reference to a 6-month period prior to the Screening Visit; or

d Answers “yes” on any items in the Suicidal Ideation section of the C-SSRS at the Baseline Visit since the last visit (Screening Visit).

 
17. Involved directly or indirectly in the conduct and administration of this study as an Investigator, sub-investigator, study coordinator, or other study staff member, or the patient is a first-degree family member, significant other, or relative residing with one of the above persons involved directly or indirectly in the study.
			
Test Product, Dose and Mode of Administration: The starting dose will be 2 mg. Planned dose cohorts are 2, 4, 8,16, and 32 mg. The dosage form will be a lyophilized powder for reconstitution for solution for injection. The route of administration of the reconstituted study drug in solution will be IT injection by direct lumbar puncture.			
Reference Therapy, Dose, and Mode of Administration: Placebo will be 0.9% Sodium Chloride Injection, sterile, preservative-free solution. Placebo will be visually identical in appearance to the WVE-120101 injection solution and administered intrathecally in order to maintain the blind.			

Sponsor: Wave Life Sciences	Investigational Product: WVE-120101	Phase: 1b/2a	EudraCT Number: 2016-005095-10
Study Duration: Doses for the 2, 4, 8, and 16 mg dose cohorts will be administered on Days 1, 56, 84, and 112, with an additional 14-week follow-up. Doses for the 32 mg cohort will be administered on Days 1, 28, 56, and 84, with an additional 14-week follow-up.			

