#### 4.1.4 Multiple-Dose Phase

The Dose Escalation Committee will determine if a dose cohort can proceed to multiple dosing.

Patients who participated in the single-dose portion of the study must complete the 8-week washout period (2, 4, 8, and 16 mg cohorts) or 4-week follow-up period before receiving additional doses. Patients will visit the clinic on Day 56 (2, 4, 8, and 16 mg cohorts) or Day 28 (32 mg cohort only) for the first of 3 monthly IT doses (Days 56, 84, and 112 or Days 28, 56, and 84) (Table 1 and Table 2).

Patients who are enrolled into the multiple-dose portion of the study only will undergo the Prescreening (Visit 1) and Screening (Visit 2) visits. Patients in the 2, 4, 8, and 16 mg cohorts will not participate in Visits 3 through 7, and will receive their first dose on Visit 8. Patients will return for 2 additional doses (Visit 9 and Visit 10) and for all follow-up visits (Table 3). Patients in the 32 mg cohort will not participate in Visits 3 through 6 and will receive their first dose on Visit 7. Patients will return for two additional doses (Visit 8 and Visit 9) and for all follow-up visits (Table 3).

Within 1 week prior to each lumbar puncture, a blood sample will be tested locally for platelet count and prothrombin time to confirm that it is safe to proceed with the lumbar puncture (Section 8.2.6). Other predose assessments may also be performed up to 1 week prior to dosing, as specifically listed in Table 1, Table 2, and Table 3.

Immediately after study drug administration, all patients should be ambulatory and active for approximately 30 minutes postdose. The Investigator should note any subtle weakness or fatigue during this period. Formal physical examinations targeting the neurological system, will be performed at the time points noted in the Schedule of Assessments (Table 1, Table 2, and Table 3). Any postdose SAEs will be monitored until resolution.

Following each dose, patients will remain in the clinic for a minimum of 4 hours postdose for safety monitoring. In addition, patients will be assessed for safety, PK, PD, and clinical effects.

The SMC will periodically review unblinded, aggregate safety data (Section 4.3.1).

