## **4.2 SCHEDULE OF ASSESSMENTS**

The schedule of assessments for patients participating in the single and multiple dose portions of the study is presented in [Table 1](#) (2, 4, 8, and 16 mg cohorts) and [Table 2](#) (32 mg cohort). The Schedule of Assessments for patients participating in the multiple-dose portion of the study only is presented in [Table 3](#).

**At each relevant time point, the UHDRS, PBA-s, and Columbia-Suicide Severity Rating Scale (C-SSRS) should be performed prior to other assessments.**

**Table 1 Schedule of Assessments for Patients Participating in Both the Single and Multiple Dose Portions of the Study (2, 4, 8, and 16 mg cohorts)**

Visit	Pre-Screening a	Screening b	Double-Blind Treatment (Single Dose)		Sentinel Patient Follow-up	Follow-up		Double-Blind Treatment (Multiple Dose)			Follow-up		
	1	2	3	4	5	6	7	8 c	9	10	11 or ET	12	13
Week		-4 to 0	0	0	0	2	4	8	12	16	20	28	30
Study Day (Visit Window, if applicable) Event/Assessment		Day -28 to -1	Day -6 to Day 1 (Baseline)	Day 2 (24 ± 4h postdose)	Day 3 (48 ± 4h postdose)	Day 14 (±2)	Day 28 (±3)	Day 56 (±3)	Day 84 (±3)	Day 112 (±3)	Day 140 or ET (±5)	Day 196 (±5)	Day 210 d (EOS) (±5)
Predose/Non-dosing Days													
Patient informed consent form (ICF) Signed	X	X											
Inclusion/exclusion criteria		X	X					X					
Medical history and demographics		X											
Physical examination e		X	X	X	X	X	X	X	X	X	X	X	
C-SSRS f		X	X*			X	X	X*	X*	X	X*		
UHDRS		X	X			X	X	X	X	X	X		
PBA-s		X	X			X	X	X	X	X	X		
Drug screen g		X											
Urine pregnancy test h			X*					X*	X*	X*			
Adverse event monitoring		X	X*	X q	X q	X	X	X*	X*	X*	X	X	X
Prior and concomitant medications		X	X*	X q	X q	X	X	X*	X*	X*	X	X	X
3T MRI of the brain (without contrast)		X					X				X		
Vital signs i		X	X*	X	X	X	X	X*	X*	X*	X	X	
12-lead ECG j		X					X						
Serum pregnancy test h		X											
Clinical laboratory tests k		X	X	X	X	X	X	X	X	X	X	X	
Hepatitis (HBsAg, HCV)		X											
Blood sample for Prescreening assays l	X												
Blood sample for PK m			X	X	X	X	X	X	X	X	X		
Blood sample for immunogenicity n			X				X	X	X	X	X	X	
CSF sample for safety, exposure, and PD o			X*				X	X*	X*	X*	X r	X	
Randomization			X										

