- a Prescreening is only required for patients who do not have documented heterozygosity for SNP rs362307 (SNP1) with the T variant on the same allele as the cytosine-adenine-guanine (CAG) triplet expansion. Prescreening can happen anytime before Screening. It is anticipated that it will take at least 6 weeks to process the results of this testing.
- b Screening assessments can occur on multiple days, provided they are within the 4-week Screening period.
- c There is a minimum washout period of 8 weeks between the first dose and the start of multiple dosing. However, due to the timing of Dose Escalation Committee review to determine if the multiple dose phase can proceed for a dose cohort, the duration between the Week 4 visit and Week 8 visit may be longer than 4 weeks. Investigators will be notified when the Visit 8/Week 8 visit can occur. During this time, a telephone contact for safety follow-up should be performed monthly, at a minimum.
- d Follow-up Day 210 Visit for AE monitoring can be a telephone call.
- e At Screening, physical examination will include (but is not limited to) an examination of skin; head, eyes, ears, nose, throat; respiratory; cardiovascular; gastrointestinal; endocrine, metabolic; blood, lymphatic; musculoskeletal, psychiatric, and neurologic systems. Predose and on Visits 6 (Day 14), 7 (Day 28), 11 (Day 140), and 12 (196) the physical exam must include (at a minimum) head, eyes, ears, nose, throat, respiratory, cardiovascular, gastrointestinal, musculoskeletal, psychiatric, and neurologic systems. Other systems should be evaluated as appropriate. After study drug administration, a targeted physical exam, including the neurologic system (with special attention to the motor system, upper and lower extremity measures of strength, tone, reflexes, and ambulation),

- will be performed 30 minutes ( $\pm 5$  minutes), 1, 2, 3, and 4 hours ( $\pm 15$  minutes) postdose, with an additional exam 24 hours ( $\pm 4$  hours) after the first dose. The sentinel patients in each cohort will also repeat this exam at 8 hours ( $\pm 30$  minutes), 12 hours ( $\pm 2$  hours), 24, and 48 hours ( $\pm 4$  hours).
- f C-SSRS baseline/screening version will be performed at the Screening Visit, and the 'since last visit' version will be performed at all other noted visits.
  - g Urine drug screen for selected drugs of abuse.

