Abbreviations: AE = adverse event; CAG = cytosine-adenine-guanine; CSF = cerebrospinal fluid; C-SSRS = Columbia-Suicide Severity Rating Scale; ECG = electrocardiogram; EOS = end of study; ET = early termination; h = hour; HBsAg = hepatitis B surface antigen; HCV = hepatitis C virus; ICF = informed consent form; IT = intrathecal; MRI = magnetic resonance imaging; PBA-s = Short Problem Behaviors Assessment; PD = pharmacodynamics; PK = pharmacokinetics; SNP= single nucleotide polymorphism; SNP1 = SNP rs362307; T= thymine; UHDRS = Unified Huntington’s Disease Rating Scale.

Note: The UHDRS, PBA-s, and C-SSRS should be completed prior to any other assessments. Assessments completed predose on Day 1 are considered Baseline.

**\*For each dosing visit (Day 1/Visit 3 [single dose phase]; Day 28/Visit 7; Day 56/Visit 8; and Day 84/Visit 9 [multiple dose phase]), these predose procedures must be performed predose on the day of dosing. All other predose assessments (inclusion/exclusion criteria [Day 1/Visit 3 and Day 28/Visit 7 only], physical examination, UHDRS, PBA-S, clinical laboratory tests [including a blood sample to confirm platelet count and prothrombin clotting time], blood sample for PK, and blood sample for immunogenicity) may be performed up to a week prior to dosing.**

- a Prescreening is only required for patients who do not have documented heterozygosity for SNP rs362307 (SNP1) with the T variant on the same allele as the cytosine-adenine-guanine (CAG) triplet expansion. Prescreening can happen anytime before Screening. It is anticipated that it will take at least 6 weeks to process the results of this testing.
- b Screening assessments can occur on multiple days, provided they are within the 4-week Screening period.
- c There is a minimum follow-up period of 4 weeks between the first dose and the start of multiple dosing. However, due to the timing of Dose Escalation Committee review to determine if the multiple dose phase can proceed for a dose cohort, the duration between the Week 4 visit and Week 7 visit may be longer than 4 weeks. Investigators will be notified when the Visit 7/Week 4 visit can occur. During this time, a telephone contact for safety follow-up should be performed monthly, at a minimum.
- d Follow-up Day 182 Visit for AE monitoring can be a telephone call.

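### The ±3-day windows for the second dose open before the stated minimum interval from the first dose (8 weeks; 4 weeks at 32 mg) has passed

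*Combined protocol and SAP*

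**What the plan says.** The interval between the first dose and the start of multiple dosing is stated as a minimum in three places:

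- Table 1, footnote c (2, 4, 8 and 16 mg cohorts): "There is a minimum washout period of 8 weeks between the first dose and the start of multiple dosing".
- Table 2, footnote c (32 mg cohort): "There is a minimum follow-up period of 4 weeks between the first dose and the start of multiple dosing".
- Section 4.1.4, on patients coming from the single-dose portion: they "must complete the 8-week washout period (2, 4, 8, and 16 mg cohorts) or 4-week follow-up period before receiving additional doses".

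The dosing days are in the Study Duration entry of the synopsis: "Doses for the 2, 4, 8, and 16 mg dose cohorts will be administered on Days 1, 56, 84, and 112", and "Doses for the 32 mg cohort will be administered on Days 1, 28, 56, and 84". The column headings of the schedule add a window to the second dose: Day 56 (±3) at Visit 8 in Table 1 and Day 28 (±3) at Visit 7 in Table 2. Footnote c is attached to those same two columns.

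On departures from the nominal day, footnote c of Table 1 says only that "the duration between the Week 4 visit and Week 8 visit may be longer than 4 weeks", because of the timing of the Dose Escalation Committee review, and that "Investigators will be notified when the Visit 8/Week 8 visit can occur". Table 2 has a parallel statement for Visit 7.

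**The concern.** A minimum interval is a floor, while a symmetric window around the same time point allows visits on both sides of it. Here both apply to the same dosing visit, so a second dose can lie inside the printed window and still come before the stated minimum. Footnote c deals with intervals that run longer and does not address the early side.

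The interval has a stated purpose. Section 2.1 ties the 8 weeks to drug levels at the end of the recovery period in the 13-week monkey study. It ties the 4 weeks at 32 mg to the observation that most treatment-emergent events occur within 28 days of the first dose. A window that opens before the interval has passed does not match that reasoning. In practice, sites and monitors could also disagree on whether an in-window dose given before the minimum is a protocol deviation.

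**Working it through.** **Inputs**

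- Minimum: 8 weeks = 8 × 7 = 56 days (Table 1, footnote c); 4 weeks = 4 × 7 = 28 days (Table 2, footnote c).
- Window for the second dose: Day 56 ± 3 = Days 53 to 59 (Table 1, Visit 8); Day 28 ± 3 = Days 25 to 31 (Table 2, Visit 7).
- Day numbering: the first dose is on Day 1, and the next visit is headed "Day 2 (24 ± 4h postdose". Day N is therefore N − 1 days after the first dose.
- Week labels: Tables 1 and 2 put the Day 1 dose in Week 0, Day 28 in Week 4 and Day 56 in Week 8.

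**Reproducing the plan's own figure.** Two counts are possible.

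- Table convention (Week 8 is Day 56, Week 4 is Day 28): the nominal visit meets the minimum exactly.
- Strict elapsed days from Day 1: the nominal visit gives 56 − 1 = 55 days against 56, and 28 − 1 = 27 days against 28. Each is 1 day short. The minimum is first reached on Day 57 (1 + 56) and Day 29 (1 + 28).

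**Early edge of the window**

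| Cohorts | Count | Interval at early edge | Minimum | Shortfall | Window days before the minimum |
|---|---|---|---|---|---|
| 2–16 mg | Table convention | Day 53 | Day 56 | 3 days (3/56 = 5%) | 53, 54, 55 (3 of 7) |
| 2–16 mg | Strict | 53 − 1 = 52 days | 56 days | 4 days (4/56 = 7%) | 53 to 56 (4 of 7) |
| 32 mg | Table convention | Day 25 | Day 28 | 3 days (3/28 = 11%) | 25, 26, 27 (3 of 7) |
| 32 mg | Strict | 25 − 1 = 24 days | 28 days | 4 days (4/28 = 14%) | 25 to 28 (4 of 7) |

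Three of the four days come from the minus side of the window and remain under either count. The fourth depends on counting from Day 1.

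**Does committee release act as a floor?** Under Section 4.3.3 the Dose Escalation Committee reviews once all patients have completed Day 28 (Day 14 at 32 mg). For the last patient dosed in a cohort, that leaves 53 − 28 = 25 days before the window opens at 2–16 mg, and 25 − 14 = 11 days at 32 mg. Release before the early edge is therefore possible. No minimum elapsed interval is among the release conditions.

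**Later doses.** Nominal spacing is 84 − 56 = 28 and 112 − 84 = 28 days (56 − 28 and 84 − 56 at 32 mg). The 1-day nominal difference thus arises only between the first and second doses.

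**The case against.** The strongest reply is that the two rules are compatible. A window permits and a minimum requires, and dosing on Days 57 to 59 (Days 29 to 31 at 32 mg) meets both even on the strict count. Because footnote c sits on the visit column, it can be read as qualifying the general ±3 days. Sites also cannot choose the early edge unprompted: they wait for notification, which follows committee review and endorsement by the chair of the Safety Monitoring Committee. From 4 mg upward it also requires that at least half of the previous cohort has had at least two multiple-phase doses. Since patients in a cohort are dosed in sequence, those dosed early will usually wait longer than the minimum.

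Most of this stands. A reader might infer that the rules cannot both be followed; the documents do not support that, because the late part of the window satisfies both. A reader might also infer that every roll-over patient will be re-dosed early. The schedule permits it but gives no reason to expect it. The 4-day figure should not stand alone either: Section 4.1.4 itself follows the washout requirement by calling patients in on Day 56 or Day 28, so the protocol treats those days as the end of the period.

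The reply does not supply the missing rule. No text says that footnote c overrides the window, that the window is one-sided at this visit, or that release depends on elapsed days.

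**Conclusion.** The inconsistency is real and small. The printed windows allow the second dose before the stated minimum under either way of counting: by 3 days (3 of 7 window days) on the tables' own week labels, and by up to 4 days (4 of 7) if elapsed days are counted strictly from a Day 1 dose. It is proportionally largest at 32 mg, at 11% or 14% of the interval. It concerns patients who continue from the single-dose portion, in all five cohorts. How many would be dosed early cannot be told from the documents.

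A reader might go further and expect affected patients to drop out of the Per Protocol population used for clinical effects. That is not supported: nothing classes an in-window dose as a major deviation, and Section 10.3.4 leaves grading to a blinded review before unblinding. The primary safety analysis uses the Safety population, which does not depend on visit timing. The sample-size statement in Section 10.2 does not use the dosing interval. The case for changing the text is that a mandatory minimum between doses should agree with the days on which dosing is permitted.

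**What to change.** Reconcile footnote c of Tables 1 and 2, Section 4.1.4 and the windows for Visit 8 (Table 1) and Visit 7 (Table 2), so that the earliest permitted dosing day and the stated minimum agree. Either the window or the minimum can be reworded; the clinical team decides which figure stands. State how the interval is counted from the first dose, since Day 1 numbering and the week labels differ by one day. While footnote c of Table 2 is open, correct its reference to a Week 7 visit: that table has no Week 7, and Visit 7 is at Week 4.

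The cost is wording in two footnotes, two column headings and one section, and at most a slightly narrower scheduling window for one visit.

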**Table 3 Schedule of Assessments for Treatment-Naïve Patients in the Multiple-Dose Portion of the Study**

Visit	Pre-Screening a	Screening b	Double-Blind Treatment (Multiple Dose)			Follow-up		
	1	2	8 (7 g )	9 (8 g )	10 (9 g )	11 (10 g ) or ET	12 (11 g )	13 (12 g )
Week		-4 to 0	8 (4 g )	12 (8 g )	16 (12 g )	20 (16 g )	28 (24 g )	30 (26 g )
Study Day (Visit Window, if applicable) Event/Assessment		Day -28 to -1	Day 56 (28 g ) (±3) (Baseline)	Day 84 (56 g ) (±3)	Day 112 (84 g ) (±3)	Day 140 (112 g ) or ET (±5)	Day 196 (168 g ) (±5)	Day 210 e (182 g ) (EOS) (±5)
Predose/Non-dosing Days								
Patient informed consent form (ICF) Signed	X	X						
Inclusion/exclusion criteria		X	X					
Medical history and demographics		X						
Physical examination d		X	X	X	X	X	X	
C-SSRS c		X	X*	X*	X	X*		
UHDRS		X	X	X	X	X		
PBA-s		X	X	X	X	X		
Drug screen f		X						
Urine pregnancy test e			X*	X*	X*			
Adverse event monitoring		X	X*	X*	X*	X	X	X
Prior and concomitant medications		X	X*	X*	X*	X	X	X
3T MRI of the brain (without contrast)		X				X		
Vital signs h		X	X*	X*	X*	X	X	
12-lead ECG i		X						
Serum pregnancy test e		X						
Clinical laboratory tests j		X	X	X	X	X	X	
Hepatitis (HBsAg, HCV)		X						
Blood sample for Prescreening assays k	X							
Blood sample for PK l			X	X	X	X		
Blood sample for immunogenicity m			X	X	X	X	X	
CSF sample for safety, exposure, and PD n			X*	X*	X*	X p	X	
Treatment Assignment								
Study drug administration via IT injection o			X	X	X			
Postdose on Dosing Days								
Physical examination d			X	X	X			
Adverse event monitoring			X	X	X			

	Pre-Screening a	Screening b	Double-Blind Treatment (Multiple Dose)			Follow-up		
Visit	1	2	8 (7 a )	9 (8 a )	10 (9 a )	11 (10 a ) or ET	12 (11 a )	13 (12 a )
Week		-4 to 0	8 (4 a )	12 (8 a )	16 (12 a )	20 (16 a )	28 (24 a )	30 (26 a )
Study Day (Visit Window, if applicable) Event/Assessment		Day -28 to -1	Day 56 (28 a ) (±3) (Baseline)	Day 84 (56 a ) (±3)	Day 112 (84 a ) (±3)	Day 140 (112 a ) or ET (±5)	Day 196 (168 a ) (±5)	Day 210 c (182 a ) (EOS) (±5)
Clinical laboratory tests d			X	X	X			
Concomitant medications			X	X	X			
Vital signs h			X	X	X			
Blood samples for PK i					X			
Study completion								X

Abbreviations: AE = adverse event; CAG = cytosine-adenine-guanine; CSF = cerebrospinal fluid; C-SSRS = Columbia-Suicide Severity Rating Scale; ECG = electrocardiogram; EOS = end of study; ET = early termination; h = hour; HBsAg = hepatitis B surface antigen; HCV = hepatitis C virus; ICF = informed consent form; IT = intrathecal; MRI = magnetic resonance imaging; PBA-s = Short Problem Behaviors Assessment; PD = pharmacodynamics; PK = pharmacokinetics; SNP= single nucleotide polymorphism; SNP1 = SNP rs362307; T= thymine; UHDRS = Unified Huntington’s Disease Rating Scale.

Note: The UHDRS, PBA-s, and C-SSRS should be completed prior to any other assessments. Assessments completed predose on Day 56 (Day 28 for the 32 mg cohort) are considered Baseline.

Patients who are treatment-naïve for the multiple-dose portion of the study will undergo Prescreening and Screening, and then receive their first dose on Day 56 (Visit 56).

**\*For each dosing visit during the multiple dose phase, these predose procedures must be performed predose on the day of dosing. All other predose assessments (inclusion/exclusion criteria [Day 56/Visit 8 for 2, 4, 8, and 16 mg cohorts or Day 28/Visit 7 for 32 mg cohort], physical examination, UHDRS, PBA-S, clinical laboratory tests [including a blood sample to confirm platelet count and prothrombin clotting time], blood sample for PK, and blood sample for immunogenicity) may be performed up to a week prior to dosing.**

- a Prescreening is only required for patients who do not have documented heterozygosity for SNP rs362307 (SNP1) with the T variant on the same allele as the cytosine-adenine-guanine (CAG) triplet expansion. Prescreening can happen anytime before Screening. It is anticipated that it will take at least 6 weeks to process the results of this testing.
- b Screening assessments can occur on multiple days, provided they are within the 4-week Screening period.
- c Follow-up Day 210 Visit (Day 182 Visit for the 32 mg cohort) for AE monitoring can be a telephone call.
- d At Screening, physical examination will include (but is not limited to) an examination of skin; head, eyes, ears, nose, throat; respiratory; cardiovascular; gastrointestinal; endocrine, metabolic; blood, lymphatic; musculoskeletal, psychiatric, and neurologic systems. Predose and on Visit 11/Day 140 and Visit 12/Day 196 for the 2, 4, 8, and 16 mg cohorts and Visit 10/Day 112 and Visit 11/Day 168 for the 32 mg cohort, the physical exam must include (at a minimum) head, eyes, ears, nose, throat, respiratory, cardiovascular, gastrointestinal, musculoskeletal, psychiatric, and neurologic systems. Other systems should be evaluated as appropriate. After study drug administration, a targeted physical exam, including the neurologic system (with special attention to the motor system, upper and lower extremity measures of strength, tone, reflexes, and ambulation), will be performed 30 minutes (±5 minutes), 1, 2, 3, and 4 hours (±15 minutes) postdose.
- e C-SSRS baseline/screening version will be performed at the Screening Visit, and the ‘since last visit’ version will be performed at all other noted visits.
- f Urine drug screen for selected drugs of abuse.
- g For female patients of childbearing potential, a negative serum pregnancy test must be documented at the Screening Visit. On dosing days, a negative urine pregnancy test must be documented predose.
- h Vital signs include blood pressure, pulse, temperature, weight, and height. On dosing days blood pressure and pulse will be measured at the following time points: ≤30 minutes predose and 1, 2, and 4 hours (±15 minutes) postdose. Weight and temperature will only be measured predose on dosing days. Height will be measured at baseline only. Blood pressure (systolic and diastolic), temperature, and pulse should be measured after patient has been resting quietly for ≥3 minutes.
- i Electrocardiogram recordings will be obtained in triplicate in the supine position after the patient has rested comfortably for ≥5 minutes.
- j Clinical laboratory safety testing, including clinical chemistry, hematology, and urinalysis. Within 1 week prior to lumbar puncture, a blood sample will be tested to confirm platelet count and prothrombin clotting time. Clinical laboratory safety testing will be performed predose on all dosing days. On Day 56 (Day 28 for 32 mg cohort) only, samples for clinical chemistry and hematology measures (CBC, complement, and fibrinogen only) will also be collected at 1 and 4 hours (±15 minutes) postdose. On all non-dosing days, clinical laboratory safety testing will be performed just

- once. On Day 196 (Day 168 for 32 mg cohort), only platelet count and prothrombin clotting time need to be assessed (prior to CSF sample). Urinalysis will be performed predose on all dosing days, and once on all other days noted.
- k Blood samples for the Prescreening assays to determine eligibility.
  - l On Day 56 (Day 28 for 32 mg cohort), all patients will have blood samples collected for PK analysis predose and 30 minutes ( $\pm 5$  minutes), 1, 2, 4 hours ( $\pm 15$  minutes) postdose. On Day 112 (Day 84 for the 32 mg cohort), all patients will have blood samples collected for PK analysis predose and 1, 2, and 4 hours ( $\pm 15$  minutes) postdose. On all other dosing days, PK samples will be collected predose only. On non-dosing days noted, PK will be collected once.
  - m Blood sample for assessment of antibodies to WVE-120101 will be obtained predose (within 1 week prior to injection) or on non-dosing days, as indicated.
  - n On dosing days, CSF sample will be collected  $\leq 15$  minutes prior to study drug administration. No more than 10 mL of CSF total should be collected. CSF samples must be tested locally for safety for the following parameters: total protein, glucose and cell counts (white blood cell counts with differential) on all noted visits.
  - o Immediately after study drug administration, patients should be active for approximately 30 minutes postdose.
  - p This lumbar puncture is optional for patients who terminate early.
  - q Visit, week, and day for the 32 mg cohort.

